5.1.3 Subject Exclusion Criteria for Randomization

The subject must be excluded from randomization in the trial if the subject:

- 1. Is currently participating and receiving study therapy with potential anti-neoplastic activity, or has participated in a study of an investigational agent and received study therapy with potential anti-neoplastic activity within 4 weeks of the first dose of treatment.
- 2. Has a diagnosis of immunodeficiency or is receiving systemic steroid therapy or any other form of immunosuppressive therapy within 7 days prior to the first dose of trial treatment.
- 3. Has a known history of active TB (Bacillus Tuberculosis)
- 4. Hypersensitivity to pembrolizumab or any of its excipients.
- 5. Has had a prior anti-cancer monoclonal antibody (mAb) within 4 weeks prior to study Day 1 or who has not recovered (i.e., ≤ Grade 2 or at baseline) from adverse events due to agents administered more than 4 weeks earlier.
- 6. Has had prior chemotherapy, targeted small molecule therapy, or radiation therapy within 2 weeks prior to study Day 1 or who has not recovered (i.e., ≤ Grade 2 or at baseline) from adverse events due to a previously administered agent.

- Note: If subject received major surgery, they must have recovered adequately from the toxicity and/or complications from the intervention prior to starting therapy.
- 7. Has a known additional malignancy that is progressing or requires active treatment other than adjuvant hormonal therapy. Exceptions include basal cell carcinoma of the skin or squamous cell carcinoma of the skin or in situ cervical cancer.
- 8. Has active autoimmune disease that has required systemic treatment in the past 2 years (i.e. with use of disease modifying agents, corticosteroids or immunosuppressive drugs). Replacement therapy (eg., thyroxine, insulin, or physiologic corticosteroid replacement therapy for adrenal or pituitary insufficiency, etc.) is not considered a form of systemic treatment.
- 9. Has known history of, or any evidence of active, non-infectious pneumonitis.
- 10. Has an active infection requiring systemic therapy.
- 11. Has a history or current evidence of any condition, therapy, or laboratory abnormality that might confound the results of the trial, interfere with the subject's participation for the full duration of the trial, or is not in the best interest of the subject to participate, in the opinion of the treating investigator.
- 12. Has known psychiatric or substance abuse disorders that would interfere with cooperation with the requirements of the trial.
- 13. Is pregnant or breastfeeding, or expecting to conceive or father children within the projected duration of treatment with pembrolizumab, starting with the pre-screening or screening visit through 120 days after the last dose of trial treatment.
- 14. Has received prior therapy with an anti-PD-1, anti-PD-L1, or anti-PD-L2 agent.
- 15. Has a known history of Human Immunodeficiency Virus (HIV) (HIV 1/2 antibodies).
- 16. Has known active Hepatitis B (e.g., HBsAg reactive) or Hepatitis C (e.g., HCV RNA [qualitative] is detected).
- 17. Has received a live vaccine within 30 days of planned start of study therapy.

Note: Seasonal influenza vaccines for injection are generally inactivated flu vaccines and are allowed; however intranasal influenza vaccines (e.g., Flu-Mist®) are live attenuated vaccines, and are not allowed.

5.2 Trial Treatments

The treatment to be used in this trial is outlined below in Table 2 and will be only be administered to subjects randomized to the experimental arm.

NCT02882282

Table 2 Trial Treatment

Drug	Dose	Dose	Route of	Number of	Treatment
		Frequency	Administration	doses	group
Pembrolizumab	200 mg	Q3W	IV infusion	4	Experimental

5.2.1 Dose Selection/Modification

5.2.1.1 Dose Selection

The rationale for selection of doses to be used in this trial is provided in Section 4.0 – Background and Rationale.

Details on preparation and administration of pembrolizumab (MK-3475) are provided in the Pharmacy Manual.

5.2.1.2 Dose Modification

Adverse events (both non-serious and serious) associated with pembrolizumab exposure may represent an immunologic etiology. These adverse events may occur shortly after the first dose or several months after the last dose of treatment. Pembrolizumab must be withheld for drug-related toxicities and severe or life-threatening AEs as per Table 3 below. See Section 5.6.1 and Events of Clinical Interest Guidance Document for supportive care guidelines, including use of corticosteroids.

Table 3

Dose Modification Guidelines for Drug-Related Adverse Events

Toxicity	Hold Treatment For Grade	Timing for Restarting Treatment	Discontinue Subject
Diarrhea/Colitis	2-3	Toxicity resolves to Grade 0-1.	Toxicity does not resolve within 12 weeks of last dose or inability to reduce corticosteroid to 10 mg or less of prednisone or equivalent per day within 12 weeks.
	4	Permanently discontinue	Permanently discontinue
AST, ALT, or	2	Toxicity resolves to Grade 0-1	Toxicity does not resolve within 12 weeks of last dose.
Increased Bilirubin	3-4	Permanently discontinue (see exception below) ¹	Permanently discontinue
Type 1 diabetes mellitus (if new onset) or	T1DM or 3-4	Hold pembrolizumab for new onset Type 1 diabetes mellitus or Grade 3-4 hyperglycemia associated with evidence of	Resume pembrolizumab when patients are clinically and metabolically stable.

NCT02882282

Toxicity	Hold Treatment For Grade	Timing for Restarting Treatment	Discontinue Subject							
Hyperglycemia		beta cell failure.								
Hypophysitis	2-3	Toxicity resolves to Grade 0-1	Toxicity does not resolve within 12 weeks of last dose or inability to reduce corticosteroid to 10 mg or less of prednisone or equivalent per day within 12 weeks.							
	4	Permanently discontinue	Permanently discontinue							
Hyperthyroidism	3	Toxicity resolves to Grade 0-1	Toxicity does not resolve within 12 weeks of last dose or inability to reduce corticosteroid to 10 mg or less of prednisone or equivalent per day within 12 weeks.							
	4	Permanently discontinue	Permanently discontinue							
Hypothyroidism	2-4	Therapy with pembrolizumab can be continued while treatment for the thyroid disorder is instituted	Therapy with pembrolizumab can be continued while treatment for the thyroid disorder is instituted.							
Infusion Reaction	3-4	Permanently discontinue	Permanently discontinue							
Pneumonitis	umonitis 2 Toxicity resolves to Grade 0-1		Toxicity does not resolve within 12 weeks of last dose or inability to reduce corticosteroid to 10 mg or less of prednisone or equivalent per day within 12 weeks.							
	3-4	Permanently discontinue	Permanently discontinue							
Renal Failure or Nephritis	Renal Failure or 2 Toxicity resolves to Grade 0-1		Toxicity does not resolve within 12 weeks of last dose or inability to reduce corticosteroid to 10 mg or less of prednisone or equivaler per day within 12 weeks.							
-	3-4	Permanently discontinue	Permanently discontinue							
All Other Drug- Related Toxicity ²	3 or Severe	Toxicity resolves to Grade 0-1	Toxicity does not resolve within 12 weeks of last dose or inability to reduce corticosteroid to 10 mg or less of prednisone or equivalent per day within 12 weeks.							
•	4	Permanently discontinue	Permanently discontinue							

Note: Permanently discontinue for any severe or Grade 3 drug-related AE that recurs or any life-threatening event.

Dosing interruptions are permitted in the case of medical / surgical events or logistical reasons not related to study therapy (e.g., elective surgery, unrelated medical events, patient vacation, and/or holidays). Subjects should be placed back on study therapy within 6 weeks of the scheduled interruption, unless otherwise discussed with the Principal Investigator. The reason for interruption should be documented in the patient's chart. There will be no dose reduction permitted in this study.

5.2.2 Timing of Dose Administration

Trial treatment should be administered on Day 1 of each cycle after all procedures/assessments have been completed as detailed on the Trial Flow Chart (Section 6.0). Trial treatment may be administered up to 7 days before or after the scheduled Day 1 of each cycle.

All trial treatments will be administered on an outpatient basis.

Pembrolizumab 200 mg will be administered as a 30 minute IV infusion.

¹ For patients with liver metastasis who begin treatment with Grade 2 AST or ALT, if AST or ALT increases by greater than or equal to 50% relative to baseline and lasts for at least 1 week then patients should be discontinued.

² Patients with intolerable or persistent Grade 2 drug-related AE may hold study medication at physician discretion. Permanently discontinue study drug for persistent Grade 2 adverse reactions for which treatment with study drug has been held, that do not recover to Grade 0-1 within 12 weeks of the last dose.

The Pharmacy Manual contains specific instructions for the preparation of the pembrolizumab infusion fluid and administration of infusion solution.

5.2.3 Trial Blinding/Masking

This is an open-label trial; therefore, IND Office, investigator and subject will know the treatment administered.

5.3 Randomization or Treatment Allocation

Patients seeking treatment at MD Anderson will be screened for this trial, including patients with oral cancers or oral IEN treated or followed at the MD Anderson Head and Neck Center. Subjects may also be identified at the multidisciplinary planning conferences, or through databases maintained by the Head and Neck Program for quality improvement. Patients in these databases who have a diagnosis of oral IEN or oral cancer may be contacted by phone or mail or during their clinic visits at MD Anderson to offer participation in the study.

Study-related procedures must not commence before obtaining consent. However, results from assessments performed before obtaining informed consent that are considered "routine standard of care" (e.g., laboratory results, CT scans, etc.) may be used to determine eligibility.

Once consent is obtained, oral IEN LOH evaluation will be performed in an archival tissue specimen obtain within 12 months prior to enrollment, or in a newly obtained oral tissue specimen. Subjects do not need to meet the eligibility criteria described in sections 5.1.2 and 5.1.3 to have their tissue evaluated for LOH. LOH negative patients will continue to be observed and followed for oral cancer-free survival, but will not be eligible for treatment or randomization. Only LOH positive cases will be eligible for randomization. Patients must also meet the additional eligibility criteria described in sections 5.1.2 and 5.1.3 to be eligible for randomization.

Randomization will be performed via a centralized, web-based randomization system. Stratified randomization with dynamic allocation will be performed via the web-based database system. For randomization purposes, eligible patients will be stratified by prior cancer status (no prior cancer versus prior cancer). Within each stratum, Pocock-Simon dynamic allocation method will be applied to achieve balanced randomization with respect to smoking status (current, former and never smoker). Patients will be randomized into the pembrolizumab arm or the observation arm with equal probability. A randomization algorithm will be developed and implemented by the department of Biostatistics at M.

D. Anderson Cancer Center. Patients who are randomized will be given a unique patient number by the centralized, web-based system and assigned to a treatment arm as follows:

Arm A (Control): observation

Arm B (Experimental): pembrolizumab

5.4 Stratification

The following stratification factors will be utilized:

• Prior history of oral cancer: yes or no

5.5 Concomitant Medications/Vaccinations (allowed & prohibited)

Medications or vaccinations specifically prohibited in the exclusion criteria are not allowed during the ongoing trial. If there is a clinical indication for one of these or other medications or vaccinations specifically prohibited during the trial, discontinuation from trial therapy or vaccination may be required. The final decision on any supportive therapy or vaccination rests with the investigator and/or the subject's primary physician.

5.5.1 Acceptable Concomitant Medications

All treatments that the investigator considers necessary for a subject's welfare may be administered at the discretion of the investigator in keeping with the community standards of medical care. All concomitant medication will be recorded on the patient's electronic medical record.

5.5.2 Prohibited Concomitant Medications

Subjects are prohibited from receiving the following therapies during the Treatment Phase of this trial:

- Antineoplastic systemic chemotherapy or biological therapy (with the exception of adjuvant hormonal therapy)
- Immunotherapy not specified in this protocol
- Investigational agents with anti-neoplastic activity other than pembrolizumab
- Radiation therapy
- Live vaccines within 30 days prior to the first dose of trial treatment and while participating in the trial. Examples of live vaccines include, but are not limited to, the following: measles, mumps, rubella, varicella/zoster, yellow fever, rabies, BCG, and typhoid vaccine.
- Systemic glucocorticoids for any purpose other than to modulate symptoms from an event of clinical interest of suspected immunologic etiology. The use of physiologic doses of corticosteroids may be approved after consultation with the Principal Investigator.

Subjects who, in the assessment by the investigator, require the use of any of the aforementioned treatments for clinical management should discontinue treatment on trial. Subjects may receive other medications that the investigator deems to be medically necessary.

The Exclusion Criteria describes other medications which are prohibited in this trial.

There are no prohibited therapies during the Post-Treatment Follow-up Phase.

5.6 Rescue Medications & Supportive Care

5.6.1 Supportive Care Guidelines

Subjects should receive appropriate supportive care measures as deemed necessary by the treating investigator. Suggested supportive care measures for the management of adverse events with potential immunologic etiology are outlined below and in greater detail in the ECI guidance document. Where appropriate, these guidelines include the use of oral or intravenous treatment with corticosteroids as well as additional anti-inflammatory agents if symptoms do not improve with administration of corticosteroids. Note that several courses of steroid tapering may be necessary as symptoms may worsen when the steroid dose is decreased. For each disorder, attempts should be made to rule out other causes such as metastatic disease or bacterial or viral infection, which might require additional supportive care. The treatment guidelines are intended to be applied when the investigator determines the events to be related to pembrolizumab.

Note: if after the evaluation the event is determined not to be related, the investigator is instructed to follow the ECI reporting guidance but does not need to follow the treatment guidance (as outlined in the ECI guidance document). Refer to Section 5.2.1 for dose modification.

It may be necessary to perform conditional procedures such as bronchoscopy, endoscopy, or skin photography as part of evaluation of the event. Suggested conditional procedures, as appropriate, can be found in the ECI guidance document.

• Pneumonitis:

- o For **Grade 2 events**, treat with systemic corticosteroids. When symptoms improve to Grade 1 or less, steroid taper should be started and continued over no less than 4 weeks.
- o For **Grade 3-4 events**, immediately treat with intravenous steroids. Administer additional anti-inflammatory measures, as needed.
- o Add prophylactic antibiotics for opportunistic infections in the case of prolonged steroid administration.

• Diarrhea/Colitis:

Subjects should be carefully monitored for signs and symptoms of enterocolitis (such as diarrhea, abdominal pain, blood or mucus in stool, with or without fever) and of bowel perforation (such as peritoneal signs and ileus).

NCT02882282

- All subjects who experience diarrhea/colitis should be advised to drink liberal quantities of clear fluids. If sufficient oral fluid intake is not feasible, fluid and electrolytes should be substituted via IV infusion. For Grade 2 or higher diarrhea, consider GI consultation and endoscopy to confirm or rule out colitis.
- o For **Grade 2 diarrhea/colitis** that persists greater than 3 days, administer oral corticosteroids.
- o For **Grade 3 or 4 diarrhea/colitis** that persists > 1 week, treat with intravenous steroids followed by high dose oral steroids.
- When symptoms improve to Grade 1 or less, steroid taper should be started and continued over no less than 4 weeks.
- Type 1 diabetes mellitus (if new onset, including diabetic ketoacidosis [DKA]) or ≥ Grade 3 Hyperglycemia, if associated with ketosis (ketonuria) or metabolic acidosis (DKA)
 - o For **T1DM** or **Grade 3-4** Hyperglycemia
 - Insulin replacement therapy is recommended for Type I diabetes mellitus and for Grade 3-4 hyperglycemia associated with metabolic acidosis or ketonuria.
 - Evaluate patients with serum glucose and a metabolic panel, urine ketones, glycosylated hemoglobin, and C-peptide.

• Hypophysitis:

- For Grade 2 events, treat with corticosteroids. When symptoms improve to Grade 1 or less, steroid taper should be started and continued over no less than 4 weeks. Replacement of appropriate hormones may be required as the steroid dose is tapered.
- o For **Grade 3-4** events, treat with an initial dose of IV corticosteroids followed by oral corticosteroids. When symptoms improve to Grade 1 or less, steroid taper should be started and continued over no less than 4 weeks. Replacement of appropriate hormones may be required as the steroid dose is tapered.

• Hyperthyroidism or Hypothyroidism:

Thyroid disorders can occur at any time during treatment. Monitor patients for changes in thyroid function (at the start of treatment, periodically during treatment, and as indicated based on clinical evaluation) and for clinical signs and symptoms of thyroid disorders.

- o Grade 2 hyperthyroidism events (and Grade 2-4 hypothyroidism):
 - In hyperthyroidism, non-selective beta-blockers (e.g. propranolol) are suggested as initial therapy.

NCT02882282

• In hypothyroidism, thyroid hormone replacement therapy, with levothyroxine or liothyroinine, is indicated per standard of care.

o **Grade 3-4** hyperthyroidism

 Treat with an initial dose of IV corticosteroid followed by oral corticosteroids. When symptoms improve to Grade 1 or less, steroid taper should be started and continued over no less than 4 weeks. Replacement of appropriate hormones may be required as the steroid dose is tapered.

Hepatic:

- o For **Grade 2** events, monitor liver function tests more frequently until returned to baseline values (consider weekly).
 - Treat with IV or oral corticosteroids
- o For **Grade 3-4** events, treat with intravenous corticosteroids for 24 to 48 hours.
- When symptoms improve to Grade 1 or less, a steroid taper should be started and continued over no less than 4 weeks.

• Renal Failure or Nephritis:

- o For **Grade 2** events, treat with corticosteroids.
- o For **Grade 3-4** events, treat with systemic corticosteroids.
- When symptoms improve to Grade 1 or less, steroid taper should be started and continued over no less than 4 weeks.
- Management of Infusion Reactions: Signs and symptoms usually develop during or shortly after drug infusion and generally resolve completely within 24 hours of completion of infusion.

Table 4 below shows treatment guidelines for subjects who experience an infusion reaction associated with administration of pembrolizumab (MK-3475).

Table 4 Infusion Reaction Treatment Guidelines

NCI CTCAE Grade	Treatment	Premedication at subsequent dosing
Grade 1 Mild reaction; infusion interruption not indicated; intervention not indicated	Increase monitoring of vital signs as medically indicated until the subject is deemed medically stable in the opinion of the investigator.	None

NCI CTCAE Grade	Treatment	Premedication at subsequent dosing
Crade 2 Requires infusion interruption but responds promptly to symptomatic treatment (e.g., antihistamines, NSAIDS, narcotics, IV fluids); prophylactic medications indicated for <=24 hrs	Stop Infusion and monitor symptoms. Additional appropriate medical therapy may include but is not limited to: IV fluids Antihistamines NSAIDS Acetaminophen Narcotics Increase monitoring of vital signs as medically indicated until the subject is deemed medically stable in the opinion of the investigator. If symptoms resolve within one hour of stopping drug infusion, the infusion may be restarted at 50% of the original infusion rate (e.g., from 100 mL/hr to 50 mL/hr). Otherwise dosing will be held until symptoms resolve and the subject should be premedicated for the next scheduled dose.	Subject may be premedicated 1.5h (± 30 minutes) prior to infusion of pembrolizumab (MK-3475) with: Diphenhydramine 50 mg po (or equivalent dose of antihistamine). Acetaminophen 500-1000 mg po (or equivalent dose of antipyretic).
	Subjects who develop Grade 2 toxicity despite adequate premedication should be permanently discontinued from further trial treatment administration.	
Grade 3: Prolonged (i.e., not rapidly responsive to symptomatic medication and/or brief interruption of infusion); recurrence of symptoms following initial improvement; hospitalization indicated for other clinical sequelae (e.g., renal impairment, pulmonary infiltrates)	Stop Infusion. Additional appropriate medical therapy may include but is not limited to: IV fluids Antihistamines NSAIDS Acetaminophen Narcotics Oxygen Pressors Corticosteroids Epinephrine	No subsequent dosing
Grade 4: Life-threatening; pressor or ventilatory support indicated	Increase monitoring of vital signs as medically indicated until the subject is deemed medically stable in the opinion of the investigator. Hospitalization may be indicated. Subject is permanently discontinued from further trial treatment administration. ould be available in the room and a physician readily	

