10.5 Events of Clinical Interest Guidance Document

Please refer to separate manual provided for biospecimen collection and handling.

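### Steroid timing for diarrhea/colitis runs the wrong way: after more than 3 days at Grade 2, but only after more than 1 week at Grade 3 or 4

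*Combined protocol and SAP*

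**What the plan says.** Section 5.6.1 gives two consecutive steroid rules for diarrhea/colitis. Grade 2 reads "that persists greater than 3 days, administer oral corticosteroids". Grade 3 or 4 reads "that persists > 1 week, treat with intravenous steroids followed by high dose oral steroids".

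The section's other Grade 3-4 steroid rules have no minimum duration. For pneumonitis the text is "immediately treat with intravenous steroids. Administer additional anti-inflammatory measures, as needed"; for hypophysitis, "events, treat with an initial dose of IV corticosteroids followed by oral corticosteroids"; for hepatic events, "events, treat with intravenous corticosteroids for 24 to 48 hours". Hyperthyroidism and renal events are handled likewise, without a wait.

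Two statements limit how binding this is. Section 5.6.1 opens with "Suggested supportive care measures for the management of adverse events with potential immunologic etiology are outlined below and in greater detail", referring to a separate guidance document on events of clinical interest (ECI). Section 5.5.2 bars "Systemic glucocorticoids for any purpose other than to modulate symptoms from an event of clinical interest of suspected immunologic etiology", so steroids for a suspected immune-related event are allowed, with no minimum duration.

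**The concern.** A steroid trigger for an immune-related toxicity should come no later as the grade rises. Here it comes later. An investigator who follows the text literally would start steroids at day 4 in a patient with moderate diarrhea and hold them until after day 7 in a patient with severe or life-threatening diarrhea.

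The protocol itself treats the higher grades as more urgent. Table 6 says hospitalization is indicated at Grade 3 and calls for urgent intervention at Grade 4. Table 3 in Section 5.2.1.2 holds drug at Grade 2-3 diarrhea/colitis and stops it permanently at Grade 4. Section 5.6.1 asks investigators to watch these patients for bowel perforation. Only the steroid timing runs the other way.

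What is at stake is the safety of individual participants, who are enrolled for precancerous lesions to lower their risk of oral cancer. Section 4.2.4 justifies the trial on a carefully optimized balance of risk and benefit.

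**Working it through.** **1. The steroid rules of Section 5.6.1 side by side**

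| Disorder | Wait before steroids, Grade 2 | Wait before steroids, Grade 3-4 |
|---|---|---|
| Diarrhea/colitis | more than 3 days | more than 1 week (7 days) |
| Pneumonitis | none | none (immediate) |
| Hypophysitis | none | none |
| Hyperthyroidism | no steroid rule | none |
| Hepatic | none | none |
| Renal | none | none |

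The difference for diarrhea/colitis is 7 − 3 = 4 days. Of the other five Grade 3-4 rules, 0 of 5 have a wait. Four of those five disorders also have a Grade 2 steroid rule, and 0 of 4 have a wait. Diarrhea/colitis is the only item with a wait and the only one where the higher grade is treated later.

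**2. Which patients fall in the gap**

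- *Grade 3 or 4 from the start.* No steroid trigger is met on days 4 to 7.
- *Grade 2, worsening to Grade 3 within the first 3 days.* The Grade 2 trigger has not been reached, and the patient now falls under the longer rule. The text does not say where the clock starts. For example, after 2 days at Grade 2, the Grade 3 trigger falls after day 7 if counted from onset, or after day 2 + 7 = 9 if counted from the change of grade. Both are later than day 3.
- *Grade 2, worsening after day 3.* Oral steroids should already have started, so only the step up to intravenous treatment is delayed.

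**3. How many patients**

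Inputs: 104 patients randomized 1:1 (Section 8.2), so 104 / 2 = 52 treated. In the lung-cancer adverse event table of Section 4.2.4, 40 of 495 patients had diarrhea of any grade and 3 of 495 had Grade 3-5. The protocol gives no rate for oral lesions, so applying these rates here is an assumption.

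- Grade 3-5 rate: 3 / 495 = 0.606%; exact (Clopper-Pearson) 95% interval 0.125% to 1.761%.
- Expected cases: 52 × 0.606% = 0.32; range 52 × 0.125% = 0.07 to 52 × 1.761% = 0.92.
- Chance of at least one case: 1 − (1 − p)^52 = 1 − (0.99394)^52 = 0.27; range 0.06 to 0.60.
- Grade 1-2, for comparison: (40 − 3) / 495 = 37 / 495 = 7.5%; 52 × 7.5% = 3.9 patients.

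Two features of the source pull in opposite directions. Treatment here is only four doses, and Section 4.2.4(d) expects the short course to reduce adverse events. On the other hand, the table lists only treatment-related events seen in at least 2% of patients, so colitis reported under its own term may be missing.

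**The case against.** The best counter-argument is that this is advisory text with several safeguards around it.

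- Section 5.6.1 leaves supportive care to the treating investigator, and Section 5.5.2 lets steroids start at any time for a suspected immune-related event.
- Sections 5.2.1.2 and 5.6.1 both send the reader to the ECI guidance document for detail. Investigators would hold it, and it may give a better rule.
- A Grade 3-4 patient would already be off drug under Table 3. Section 5.6.1 also advises considering gastroenterology consultation and endoscopy from Grade 2 upward.
- The Grade 3-4 rule could be read as escalation to intravenous treatment, with oral steroids from day 3 taken for granted.
- That other organs have no wait does not show that diarrhea should have none, since infection has to be ruled out.

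Much of this stands as a limit on practical harm. None of it supplies an earlier steroid trigger for Grade 3-4. Holding drug is not treating the event. The escalation reading is not written down, because the 3-day rule is confined to Grade 2. Ruling out infection may justify some wait, but not a longer one for the more severe grade.

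The unseen document could settle the matter in practice. Sections 7.1.2.1 and 7.2.3 place it in the appendix, but its entry there (Section 10.5) says "Please refer to separate manual provided for biospecimen collection and handling". In the protocol as provided, Section 5.6.1 is therefore the only steroid timing for diarrhea/colitis. If the ECI document differs, the two conflict and one still has to be corrected. The wrong pointer is a clerical error and adds no weight to the main point.

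**Conclusion.** The concern holds, and the text should be fixed. The suggested steroid trigger comes 4 days later for Grade 3-4 diarrhea/colitis than for Grade 2, against the pattern of every other steroid rule in the section. Confidence in the reading is high: both sentences are complete, and nothing suggests a text-extraction error.

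The practical effect is small: about 0.32 expected cases of Grade 3-5 diarrhea among 52 treated patients, assuming lung-cancer rates carry over. Fewer still would be affected if investigators use their discretion to treat earlier. The case rests on the consequence for the individual patient, not on frequency. Nothing in the primary endpoint, power or statistical conclusions depends on it.

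**What to change.** Reword the Grade 3 or 4 diarrhea/colitis bullet in Section 5.6.1 so that its steroid trigger is no later than the Grade 2 trigger. The simplest version deletes the one-week wait, as in the other Grade 3-4 rules. Add that days already spent at Grade 2 count when the grade rises. The documents do not state what the right Grade 3-4 threshold is, so the clinical leads should confirm it.

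Check the new wording against the ECI guidance document, and correct the appendix entry in Section 10.5 so that it points to that document.

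The cost is two lines of protocol text and one corrected pointer, with no new procedures, patients or staff.
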